## Scotopic perimetry in Age-related Macular Degeneration

[name]

Director, Rose-Silverthorne Retinal Degenerations Laboratory

Scientific Director, Retina Foundation of the Southwest

Director of Visual Electrophysiology and Adjunct Professor of Ophthalmology

University of Texas Southwestern Medical School

Perimetry is typically used for assessing the regional variations in function for patients with retinal disease. Standard perimetry only measures cone-mediated sensitivity. Until recently, it has not been possible to obtain rod-mediated perimetry other than by custom-built devices. There are many factors, however, that make rod-mediated fields attractive. Despite their different etiologies, retinal degenerations share many common features. For example, many of the mutations causing retinitis pigmentosa are expressed in rod photoreceptors, and night blindness is often the earliest symptom. Similarly, a growing body of evidence indicates that rods are affected early in age-related macular degeneration (AMD) and Stargardt disease. In addition, some of the contemporary treatment strategies are common to these diseases. These treatment strategies require localized outcome measures of rod and cone function to evaluate treatment efficacy.

The MP-1S was the first fundus perimeter to provide highly localized measures of rod and cone function. It incorporates a fundus-tracking system and follow-up mode to maintain constant stimulus projection on the retina and facilitate repeat testing of identical loci despite eye movements. The scotopic MAIA is a more recent option for scotopic perimetry. It provides a faster test, but has a limited dynamic range. Average normal sensitivity for elderly patients with spot size 3 within the macula is approximately 15 dB, so the machine has a floor effect for patients with losses  $> 1.5$  log unit. The MP-1S has a greater dynamic range because neutral density filters can be adjusted to fit the range needed for the patient. The mean normal value for 13 elderly subjects tested to date is 23 dB for a stimulus size 3. The 8 dB difference in normal scotopic sensitivity on the two fundus perimeters is also seen in patients with macular disease. To date, we have compared 10 patients on both devices. The correlation in mean sensitivity between the two devices is high ( $r = 0.73$ ) with the Nidek MP-1S having sensitivity on average 10 dB higher than the MAIA-2S.

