The Nidek MP-3S is a next-generation fundus perimeter designed to replace the MP-1S. In general, it is easier to use than the MP-1S. It incorporates a red screen that does not interfere with the dark adaptation of the patient. Other advances include "fade-out-protection" for the fixation light to avoid the Troxler effect, which is particularly common in an otherwise dark field. Rather than the joystick on the MP-1S for aligning the patient, the MP-3S actively tracks the pupil position of the patient. Another important advantage of the MP-3S is the higher luminance of the background for standard testing. The 34 cd/m^2 background is 10 times brighter than the background of the MP-1, making it truly a photopic, rather than mesopic, test. Thus the MP-3S can be used in standard mode with a background that saturates rods and produces a cone-mediated sensitivity map, or in scotopic mode, with no background to produce a rod-mediated sensitivity field. Rather than having to insert filters as in the MP-1S, the filters in the MP-3S are fixed and

automatically moved into position when a scotopic test is specified. This leads to much greater ease of use and less possibility of technician error while running the test.

Representative normal sensitivity maps for 2 different spot sizes on the MP-3S are shown in Figure 1. For spot size 3, the values are comparable but slightly higher than for elderly subjects tested on the MP-1S (7 corresponds to 27 on the MP-1S, given the 2.0 log filter). For the larger spot size 5, values are considerably higher consistent with spatial summation. It is also important to point out that the range over which patients can be tested can be varied by adjusting spot size. There is a tradeoff between the greater spatial localization with spot size 3 and the larger dynamic range with spot size 5.

[figure not shown]

Figure 1. Comparison of spot sizes 3 and 5 on MP-3S in normal subject

In order to compare results from patients on the MP-3S to those from the MP-1S, we tested 10 patients with age-related macular degeneration using the following parameters:

Table 1 Comparison of Nidek MP-3S to Nidek MP-1S

[figure not shown]
	MP-3S	MP-1S
Mode	Scotopic	Scotopic
Pattern	NdkSctRed36p	AMD GA Rod Reduced
Test loci	32	32
Spot size	5	5
Filter	Internal	Blue+ 2.0
Fixation	3 deg circle	3 deg circle
Staircase	4:2	4:2

The patients will be greater than 55 years of age. Each patient will be evaluated with the following procedures:

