- Best-corrected visual acuity of both eyes
- Slit lamp examination to screened for a narrow angle prior to dilation
- Pupil dilation with 30 minutes patching for dark-adapted testing of the better seeing eye
- Dark-adapted visual field test on Nidek microperimeter, model MP-3S using a protocol that takes approximately 20 minutes
- Dark-adapted visual field test on Nidek microperimeter, model MP-1S using a protocol that takes approximately 20 minutes
- Imaging on Heidelberg Spectralis Optical Coherence Tomography and fundus autofluorescence unit

MP-3S and MP-1S testing order will be randomized and both tests will be conducted on the same day. Coefficients of repeatability will be obtained for each test and compared to the literature. We will determine the range of values for point sensitivity to determine the amount that a patient has to change at a given location to be significant. The limits of agreement for the two devices measuring scotopic sensitivity will be compared to limits of agreement for mesopic testing.

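### Repeatability of each device is to be compared only with the literature, although both devices are tested in the same eyes and the aim is to compare them with each other

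*Protocol*

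**What the plan says.** All of this is in the single narrative section of the Protocol, with Table 1 and the Appendix.

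- **Role of the new device:** "The Nidek MP-3S is a next-generation fundus perimeter designed to replace the MP-1S". The sentence that introduces Table 1 gives the purpose of the testing as comparing patients' results on the two instruments.
- **Design:** "MP-3S and MP-1S testing order will be randomized and both tests will be conducted on the same day". The procedure list specifies the better-seeing eye. Table 1 matches the number of loci (32), spot size (5), fixation target and staircase (4:2), and the Appendix gives one set of coordinates for both devices.
- **Repeatability:** "Coefficients of repeatability will be obtained for each test and compared to the literature". This is the only sentence on how the coefficients will be judged.
- **Agreement:** "The limits of agreement for the two devices measuring scotopic sensitivity will be compared to limits of agreement for mesopic testing".
- **Tests per patient:** the procedure list has one entry for the new device, "Dark-adapted visual field test on Nidek microperimeter, model MP-3S using a protocol that takes approximately 20 minutes", and one for the old, "Dark-adapted visual field test on Nidek microperimeter, model MP-1S using a protocol that takes approximately 20 minutes". No repeat on either device is listed.

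**The concern.** If the MP-3S is to take over from the MP-1S, users need to know whether it is about as repeatable, better or worse. The design controls the factors that would otherwise cloud that question: patient, eye, day, test pattern, spot size and staircase. A published coefficient controls none of them by design. If the MP-3S coefficient differs from a literature value, the difference may come from the device, the patients, the test settings or the retest interval, and the study cannot say which.

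The other planned analysis does not fill the gap. Between-device limits of agreement combine the noise of both devices with any patient-specific disagreement between them. They are then to be read against mesopic limits, although no mesopic test is among the listed procedures. As written, neither result has a yardstick from within the study.

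**Working it through.** The protocol gives no expected repeatability, precision target or power figure, so there is no figure of its own to reproduce. The SDs in dB below are assumptions for illustration.

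**Inputs from the Protocol:** 10 patients (sentence introducing Table 1); 32 loci (Table 1, Appendix); one listed test per device (procedure list).

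**1. What the listed schedule supports.** Within-device degrees of freedom for a patient-mean coefficient are n(k − 1), with k tests per device.
- As listed, k = 1: 10 × 0 = 0. No coefficient can be estimated, so it can be compared neither with the literature nor with the other device.
- Assuming k = 2: 10 × 1 = 10 per device. The steps on precision below use this.

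**2. Limits of agreement do not identify repeatability.** With within-device SDs s1 and s2 and a patient-by-device SD s_i:
- coefficient of repeatability: CR = 1.96 × √2 × s
- limits half-width: 1.96 × √(s1² + s2² + s_i²)

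| s1, s2, s_i (dB, assumed) | CR1, CR2 (dB) | Limits half-width (dB) |
|---|---|---|
| 2.0, 2.0, 0 | 5.54, 5.54 | 5.54 |
| 2.6, 1.11, 0 | 7.21, 3.08 | 5.54 |
| 1.0, 1.0, 2.449 | 2.77, 2.77 | 5.54 |

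The same limits fit equal devices, devices whose coefficients differ more than twofold, and two precise devices that disagree patient by patient.

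**3. The yardstick from within the study.** If the devices differed only by their own noise (s_i = 0), the half-width would be 1.96 × √(s1² + s2²). Since CR² = 1.96² × 2 × s², this equals √((CR1² + CR2²)/2). In the third row that is 2.77 dB against an actual 5.54 dB, which is the information that the limits alone do not give.

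**4. Precision of one coefficient (10 df).** The 95% interval runs from √(10/20.48) = 0.70 to √(10/3.247) = 1.76 times the estimate. A 30% gap from a published value is at the edge of sampling noise before any difference in settings.

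**5. Precision of the head-to-head ratio.** Treating the two devices' errors as independent with 10 df each, the 95% limits are the estimated ratio divided and multiplied by √F(0.975; 10, 10) = 1.93. A two-sided 5% test would have power of about 10%, 22% and 55% at true ratios of 1.25, 1.5 and 2.0.

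**6. Locus-level bound.** With one repeat, 10 × 32 = 320 locus pairs per device. If all were independent, a ratio of about 1.12 would suffice. Loci within an eye are not independent, so the answer lies between 1.12 and 1.93, and the analysis must keep the loci clustered.

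**The case against.** **The pairing is already used.** A reader might infer that the paired design is wasted. It is not: the between-device limits are a standard paired analysis and serve the stated aim. What remains is narrower, namely that the pairing is not used for repeatability and that the limits cannot stand in for it (step 2).

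**The literature comparison is legitimate, and an SAP could add the contrast.** Both are fair. Comparison with published values is a sound external check, and nothing in the text forbids setting the two coefficients side by side. But the protocol is not silent here. It names a comparator, and that comparator alone does not fit its purpose.

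**The confounding is presumed.** No published source is identified, so one can say only that settings may differ. A reader might go further and take the protocol's own remarks as proof that settings affect repeatability: "For the larger spot size 5, values are considerably higher consistent with spatial summation", and, for the older device, "The mean normal value for 13 elderly subjects tested to date is 23 dB for a stimulus size 3". Both concern the level of sensitivity, not its repeatability, and do not establish this.

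**The replacement is noisy too.** This stands. The head-to-head ratio carries sampling error on both sides. Its advantage is control of patients and settings, not precision.

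**The yardstick can be over-read.** A reader might take, say, an observed half-width of 7 dB against a noise-only 5 dB as showing real extra disagreement between the devices. With 10 patients (9 df) the SD-based 95% range for 7 dB is 0.69 to 1.83 times, or 4.8 to 12.8 dB, which includes 5 dB.

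**The missing repeat comes first.** This also stands. Changing the comparator does not create repeat tests, and any low cost claimed for the change depends on having them.

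**Conclusion.** The point holds in limited form. The only comparator named for repeatability is external, while the aim is a comparison of two devices under matched conditions in the same eyes. A gap from the literature could not be attributed to the device, and the planned limits of agreement fit very different pairs of coefficients equally well.

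The gain from the change is freedom from differences in patients and settings. It is not a decisive answer: under the assumption of 10 patients and one repeat per device, a patient-mean ratio below about 1.9 could not be told from 1. The locus-level figure lies somewhere between 1.12 and 1.93, depending on clustering that the documents do not quantify. All of it is conditional on within-device repeats, which the promise of coefficients implies and the procedure list does not show.

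**What to change.** 1. **Reconcile the text first.** The promise of a coefficient of repeatability for each device and the list of a single test on each must be made consistent.
2. **Where within-device repeats are obtained,** make the within-patient contrast the main comparison of repeatability: the ratio of the MP-3S to the MP-1S within-patient SD, with a 95% interval from resampling whole patients, so that the 32 loci stay clustered.
3. **Report it as estimation,** not as a test, and state that the interval will be wide.
4. **Read the between-device limits** against √((CR1² + CR2²)/2), with the uncertainty of both quantities shown. Compute both at the same level (patient mean or locus), with the limits based on one test per device, since averaging repeats would shrink the limits but not this yardstick.
5. **Keep the literature comparison as descriptive,** and state the spot size and staircase of each report used.

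Cost: a change of wording and one more paired analysis with a wide interval. If the repeats that the coefficients require are already intended, no further patients or tests are needed. If they are not, the cost of obtaining them belongs to the promise of repeatability itself, whichever comparator is chosen.

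### The threshold for change at a test location rests on the range of point sensitivities, not on within-patient, same-device repeatability, which the listed tests cannot supply

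*Protocol*

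**What the plan says.** The analysis is described in the short paragraph that follows the list of procedures in the protocol, under its single main heading. Three statistics are planned there, each with its own stated use.

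- **Repeatability:** "Coefficients of repeatability will be obtained for each test and compared to the literature".
- **Change threshold:** the investigators will determine the "range of values for point sensitivity to determine the amount that a patient has to change at a given location" for the change to be significant.
- **Agreement:** "The limits of agreement for the two devices measuring scotopic sensitivity will be compared to limits of agreement for mesopic testing".

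The list of procedures gives each patient one test on each device: "Dark-adapted visual field test on Nidek microperimeter, model MP-3S using a protocol that takes approximately 20 minutes" and "Dark-adapted visual field test on Nidek microperimeter, model MP-1S using a protocol that takes approximately 20 minutes". On timing it says "MP-3S and MP-1S testing order will be randomized and both tests will be conducted on the same day". No second test on the same device is mentioned. The only patient number given for this comparison is in the past tense: "we tested 10 patients with age-related macular degeneration using the following parameters".

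**The concern.** A threshold for change within a patient should answer one question: how far apart can two tests of the same eye, at the same location and on the same device, fall when nothing has changed? That depends on within-patient measurement error alone. The sentence on the change threshold instead names the range of the sensitivity values.

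Two things follow if it is applied as written. First, a range has no set coverage and tends to widen as more values are collected, so it corresponds to no particular false-positive rate. Second, with one test per device, a given location has one value per patient on that device. A range there can only run across patients, and it contains their true differences as well as error. Pooling locations would add true differences between locations.

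The protocol's introduction says that treatment strategies for these diseases need localized measures of function, so a pointwise change threshold is a result that others may use. If it depends on how varied the patients were and how many were tested, it will usually be too wide and hide real local change. With few patients it can also be too narrow by chance.

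**Working it through.** The protocol states no threshold, SD, coverage level or sample-size calculation, so there is no figure of its own to reproduce. The check has two parts.

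**1. What the listed tests can estimate**

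At one location, write a patient's result on a device as true sensitivity + device bias + patient-specific device effect + error. Let the within-patient error SD be sw3 on the MP-3S and sw1 on the MP-1S, let sb be the between-patient SD, and let sI be the SD of the patient-specific difference between devices.

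- Change on one device, MP-3S, two tests: variance of the difference = 2·sw3². This is what a change threshold needs.
- Across patients on the MP-3S, one test each: variance = sb² + sw3².
- MP-3S minus MP-1S within a patient: variance = sI² + sw3² + sw1².

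The listed tests give the second and third quantities, not the first. Extracting sw3 or sw1 from them would need added assumptions (a common scale and no patient-specific device difference) that the protocol does not state.

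**2. What a literal range would do**

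Inputs:
- n = 10 patients, from the past-tense sentence before the table of test parameters. That this is the planned number is an assumption.
- One location, independent normal values: assumed.
- sb/sw = 0, 1, 2: assumed, because the protocol gives no SDs.

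Formulas:
- 95% limit for change = 1.96 × √2 × sw = 2.77 sw, with sw treated as known.
- Ratio k = range (in SD units) × √(sb² + sw²) / (2.77 sw).
- Probability of flagging a true change of twice the limit = average of Φ(1.96 × (2 − k)) over the simulated k. At k = 1 this is Φ(1.96) = 97.5%.
- False-flag rate in an unchanged patient = average of 2 × (1 − Φ(1.96k)). At k = 1 this is 5%.

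The simulated range of 10 normal values (1,000,000 draws) averages 3.08 SD, with a 95% sampling interval of 1.67 to 4.78 SD. Mean k is therefore:

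- sb/sw = 0: 3.08 × 1 / 2.77 = 1.11
- sb/sw = 1: 3.08 × √2 / 2.77 = 1.57
- sb/sw = 2: 3.08 × √5 / 2.77 ≈ 2.48

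| sb/sw | mean k | 95% interval of k | range exceeds limit | flags change of 2 × limit | false flags |
|---|---|---|---|---|---|
| 0 | 1.11 | 0.60 to 1.73 | 63% | 93% | 5.5% |
| 1 | 1.57 | 0.85 to 2.44 | 93% | 75% | 1.3% |
| 2 | 2.48 | 1.35 to 3.86 | 99.7% | 29% | 0.1% |

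**Dependence on the number of values:** at the same SD, the mean range is 2.32 SD for 5 values, 3.08 for 10, 3.73 for 20, 4.50 for 50 and 5.02 for 100. For 32 independent values, the number of loci in the pattern, it is 4.14 SD; correlated loci would raise it less.

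**Lack of coverage:** even with sb = 0 and n = 10, the 5th and 95th percentiles of the range (1.86 and 4.47 SD) correspond to false-flag rates of 19% and 0.2%.

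**The case against.** The strongest reply is that this is loose wording. The sentence does not say maximum minus minimum, does not say across patients, and does not say that the threshold equals the range. It sits between a sentence on repeatability and one on limits of agreement, and it speaks of a patient changing at a location. A sympathetic reader would take it to mean a pointwise test-retest interval. The coverage level and the exact formula could then be left to an analysis plan that is not shown here. It can also be said that planning a coefficient of repeatability for each test implies same-device repeats, in which case the mixing of patient differences need not arise.

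Much of this stands. The intention may well have been sound. A reader might infer that the investigators will certainly use an across-patient maximum minus minimum, or that no repeat tests exist. The protocol establishes neither: it does not define the range, and its plan for repeatability sits uneasily with its list of single tests. The magnitudes are also only illustrations. The SD ratios are assumed, the number 10 comes from a past-tense sentence, and thresholds from a 4:2 staircase are only roughly normal. With no between-patient spread, the average loss is modest.

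What does not stand is that the sentence is merely short of detail. It names a basis for the threshold, while the suitable statistic in the sentence before it is given another use, comparison with the literature. If there are no repeats, a range across patients measures the wrong variation, and a difference between devices is not error within a device. If there are unlisted repeats, a literal range of them still has no fixed coverage. Either way the sentence needs rewriting.

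**Conclusion.** The point holds in this form: as written, the protocol bases its threshold for significant local change on an unsuitable statistic, does not link it to the repeatability coefficients, and lists no same-device repeat tests from which a valid threshold could be estimated. This is worth correcting, because the threshold is one of the few results the protocol promises.

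The size cannot be fixed from the document. Assuming 10 independent normal values at one location, a literal range averages about 1.1, 1.6 and 2.5 times the 95% repeatability limit at between/within SD ratios of 0, 1 and 2. The direction is usually towards missing real change, although at ratio 0 the range falls below the limit in 37% of samples (100% − 63%). It would go too far to conclude that the threshold will be wrong by any particular factor, or that 29% detection is expected; that figure belongs only to an assumed ratio of 2. No dB value can be given.

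**What to change.** Replace the sentence on the change threshold with wording such as: *The amount a patient must change at a location to be significant is the pointwise coefficient of repeatability for that device, 1.96 × √2 × within-patient SD, estimated from same-device repeat tests and allowing for loci clustered within patients.* State where the repeat tests come from, since the list of procedures does not show them.

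If no same-device repeats exist, remove the claim about how much a patient has to change. Report only the between-device pointwise limits of agreement, labelled as agreement between devices and not as a threshold for change.

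If repeats exist, the cost is wording and analysis only. If they do not, the cost is giving up a claim that the listed tests cannot support.

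### Does the planned comparison with mesopic limits of agreement lack a comparator, given that no mesopic test is performed?

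*Protocol*

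**What the plan says.** The protocol has no numbered sections. The paragraph after the procedure list closes with the sentence at issue: "The limits of agreement for the two devices measuring scotopic sensitivity will be compared to limits of agreement for mesopic testing". It gives no source, device pair or population for the mesopic limits.

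The procedure list holds six items, of which two are perimetry: "Dark-adapted visual field test on Nidek microperimeter, model MP-3S using a protocol that takes approximately 20 minutes" and "Dark-adapted visual field test on Nidek microperimeter, model MP-1S using a protocol that takes approximately 20 minutes". The analysis paragraph then adds: "MP-3S and MP-1S testing order will be randomized and both tests will be conducted on the same day". Table 1 gives the mode as scotopic on both devices.

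The background text on the MP-3S describes a standard mode and a scotopic mode. Of the standard mode it says that its "background is 10 times brighter than the background of the MP-1, making it truly a photopic, rather than mesopic, test", and that "the MP-3S can be used in standard mode with a background that saturates rods and produces a cone-mediated sensitivity map".

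Two sentences before the sentence at issue, the same paragraph says: "Coefficients of repeatability will be obtained for each test and compared to the literature".

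**The concern.** The plan commits to comparing two quantities, and the procedures generate only one of them. No listed procedure is mesopic. The obvious remedy, running both devices in standard mode, would not give a mesopic pair either: by the protocol's own account the MP-3S standard background is photopic and the MP-1 background is a tenth as bright.

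If the gap were filled with mesopic test-retest limits from a single device, unlike quantities would be compared. Limits between two devices contain any variation in how individual patients respond to one device relative to the other, and test-retest limits on one device do not. Scotopic testing could then look less precise than mesopic testing when the measurement error is the same. This matters because the sentence is the only benchmark the protocol gives for between-device agreement.

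**Working it through.** The protocol states no limits of agreement, SD or margin on this point, so there is no figure of its own to reproduce. The check is mainly a reading of the text.

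**What the study collects.** There are two perimetry tests per patient, one on each device. Both are dark-adapted and both are scotopic in Table 1. Mesopic tests: 0 of 6 listed procedures. This part of the concern is right.

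**What the standard modes could supply.** The MP-3S background is 34 cd/m², so the implied MP-1 background is 34 / 10 = 3.4 cd/m², a gap of log10(10) = 1 log unit. On the protocol's description, a standard-mode comparison of the two devices would be photopic against mesopic. This is also right, but it applies only to that device pair in those modes.

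**What the analysis sentence requires.** Its first half refers to the two devices measuring scotopic sensitivity. Its second half refers to mesopic testing in general. It does not say that mesopic limits will be obtained in this study, and it does not tie them to the same two devices. The neighbouring sentence on repeatability takes its comparator from published work. Read together, the mesopic limits are most naturally external values, and an external benchmark needs no in-study test.

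**Whether the two kinds of quantity are confused.** The paragraph uses coefficients of repeatability for each test taken singly and limits of agreement for the two devices. That usage keeps test-retest and between-device quantities apart.

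**How large the bias would be if they were confused.** The inputs here are assumptions. Let the error SD be 1.5 dB in every test, and let s be the SD that patient-by-device variation adds to the difference.

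- Single-device test-retest half-width: 1.96 × √(1.5² + 1.5²) = 1.96 × √4.5 = 4.16 dB.
- Between-device half-width: 1.96 × √(4.5 + s²).

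| s (dB) | Between-device half-width (dB) | Ratio to 4.16 |
|---|---|---|
| 0 | 1.96 × √4.5 = 4.16 | 1.00 |
| 1 | 1.96 × √5.5 = 4.60 | 1.11 |
| 2 | 1.96 × √8.5 = 5.71 | 1.37 |
| 3 | 1.96 × √13.5 = 7.20 | 1.73 |

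The result also depends on how the variation is defined. If 2 dB is the SD on each device separately, the variance of the difference gains 2 × 2² = 8 rather than 4, and the half-width is 1.96 × √12.5 = 6.93 dB. A constant offset between devices shifts the centre of the limits and leaves their width unchanged.

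With equal error SDs the direction is fixed, since any s above 0 widens the between-device limits. The size is whatever the assumed s makes it.

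**The case for a change.** The strongest case for a change is that an external source does not fully solve the problem. Between-device limits for this pair in the modes described would not be mesopic on both sides. Limits from other device pairs would differ in device and in lighting condition together, so a difference could not be attributed to either. Single-device limits are a different quantity. No later document can create mesopic data that the procedures do not collect. On this view the sentence should give way to an agreement margin in dB fixed before analysis.

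Part of this stands. The study yields no mesopic data, the source is unnamed, and the MP-3S standard mode could not be that source on the protocol's description. Confounding of device with lighting condition is a real limit on what an external comparison could show.

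The rest does not carry. The protocol states no hypothesis, margin or better-or-worse conclusion for this comparison, and it attributes no difference to device or condition. It says only that the values will be compared. Whether suitable published mesopic limits exist cannot be settled from the protocol, so their absence cannot be asserted. A fixed dB margin is a different design choice that statisticians could reasonably debate. Such a margin, like the choice of benchmark, is commonly left to a statistical analysis plan, and that plan is not at hand.

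**Conclusion.** The concern is right on its facts: there are 0 mesopic tests, and the MP-3S standard mode is described as photopic. It does not follow that the comparison has no comparator. The sentence is most naturally read as setting the scotopic between-device limits beside external mesopic values for context, as the same paragraph does for repeatability. That reading is an inference from the wording, because the protocol does not name the source.

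The possible distortion runs from 0% to 73% over assumed patient-by-device SDs of 0 to 3 dB with an assumed error SD of 1.5 dB. It arises only if test-retest limits are substituted and a conclusion on precision is drawn from them, and neither step is planned. What is left is a gap in detail that a competent analyst fills when reporting, by citing the source and saying what kind of limits are quoted and under which lighting. Removing the comparison would discard some context without correcting an error. No change to the plan is needed.
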